8.6.2. Subgroup analyses

Additional subgroup summaries will be performed for the primary endpoint to determine whether differences exist in primary endpoint results between subgroups. These subgroup summaries will be carried out using the subjects from the mITT.

The list of potential subgroups (with applicable definitions in parentheses) includes, but is not necessarily limited to, the following:

- Age (18-39, 40-64, 65+ years)
- Sex (Female vs. Male)
- History of diseases associated with, or risk factors for, prurigo nodularis, as described in
 - Dermatologic diseases;
 - Conditions associated with metabolic itch (e.g., liver, renal or endocrine);
 - Atopy (including atopic dermatitis alone, if the numbers are large enough);
 - Neurologic conditions associated with itch;
 - Other.

These medical history subgroup analyses will be performed if the smaller of the 2 groups (with or without the condition) has at least 30 subjects. Additional post-hoc subgroup evaluations may be performed if the initial observations warrant it.

For each subgroup variable, the frequency and percentage of responders for each category will be displayed by treatment group. The difference in response rate between the treatment groups and 95% CI will also be presented. These subgroup analyses will be considered exploratory, as they do not control for multiplicity.

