5. SAMPLE SIZE AND POWER

The planned sample size of approximately 240 subjects (120 per group) is based on assumed responder percentages for placebo and NAL ER of 25% and 45%, respectively. These responder percentages represent estimates based on the Week 10 data from the TR03 study. Power is set at 90% with a 2-sided significance level of 0.05.

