8. STATISTICAL METHODS AND ANALYSIS

8.1 General Statistical Conventions

All statistical procedures will be completed using SAS 9.4® or higher.

Unless otherwise stated, all statistical testing will be two-sided and will be performed using a significance (alpha) level of 0.05, and two-sided 95% confidence intervals (CI) will be provided when relevant.

Continuous variables will be summarized using descriptive statistics, including number of subjects (n), mean, median, standard deviation (SD), minimum and maximum. For efficacy variables with subscales, the total score and subscales will be summarized.

For categorical variables, summaries will include counts of subjects and percentages. Percentages will be rounded to one decimal place.

Unless otherwise stated all summaries will be presented by treatment group.

All subject data, including those derived, will be presented in individual subject data listings. Unless otherwise stated, unscheduled visit results will be included in date/time chronological order, within subject listings only. All listings will be sorted by treatment group, subject ID, date/time and visit/study day. Subject's sex and age will be stated on each listing. Unless otherwise stated, data listings will be based on All Subjects Randomized Set.

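### The subgroup section sets out to find differences between subgroups, but neither document plans an estimate or test of such a difference

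*SAP*

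**What the plan says.** SAP section 8.6.2 gives the purpose: "Additional subgroup summaries will be performed for the primary endpoint to determine whether differences exist in primary endpoint results between subgroups". The factors are age (three bands), sex, and five medical-history groups. A history group is analysed if "the smaller of the 2 groups (with or without the condition) has at least 30 subjects". For each category the section asks for the frequency and percentage of responders by arm, and adds: "The difference in response rate between the treatment groups and 95% CI will also be presented". On status it says: "These subgroup analyses will be considered exploratory, as they do not control for multiplicity". It also allows further post-hoc subgroup work if the first results suggest it, without giving a criterion.

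Nothing elsewhere supplies a comparison between categories:

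- The logistic model in SAP section 8.5.1.1 has baseline score and region.
- The sample code for the primary endpoint and the repeated-measures model in SAP section 8.6.3 contain one kind of interaction, treatment by visit.
- SAP section 8.3.2 describes the history groupings and refers to section 8.6.2 for their analysis.
- Protocol section 13.4.6 has no subgroup analysis.

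**The concern.** The aim and the output concern different null hypotheses. The aim needs the null that the NAL ER effect is the same in every category of a factor. A within-category interval addresses the null that there is no effect in that one category. Two categories with identical true effects can easily have one interval that excludes zero and one that does not, because the smaller category has less power.

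The history groups make this sharper. The entry rule lets in a group of 30 subjects, about 15 per arm, beside a complement of up to 330. A table like that invites the reading that the drug works in one group and not in the other, when the contrast may reflect little more than group size. The exploratory label does not cover this, because the reason given for it is multiplicity. Even a single factor such as sex would lack the estimate that the stated aim calls for.

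**Working it through.** **Inputs.** Planning rates are "responder percentages for placebo and NAL ER of 25% and 45%, respectively" (SAP section 5). For the level, "all statistical testing will be two-sided and will be performed using a significance (alpha) level of 0.05" (SAP section 8.1). N = 360 randomised 1:1 is from Protocol section 9.1.1; the SAP still describes 240 with a maximum of 360. The 30-subject minimum is from SAP section 8.6.2. The documents give no subgroup shares, so the splits below are assumptions, with arms balanced inside each category.

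**The plan's own figure first.** Without site, SAP section 5.2 gives 234 subjects (117 per arm) for 90% power. The usual two-proportion formula with pooled variance under the null gives
(1.96·√(2·0.35·0.65) + 1.2816·√(0.25·0.75 + 0.45·0.55))² / 0.20² = 117.4, so 118 per arm. That agrees to within 2 subjects in total. Power at 120 per arm is 0.906, against 0.90 stated.

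**Step 1: power of one category's interval.** For n per arm, SE = √((0.1875 + 0.2475)/n) = √(0.435/n). The chance that the Wald 95% CI excludes zero is about Φ(0.20/SE − 1.96).

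- n = 90: SE = 0.0695, power 0.820.
- n = 15: SE = 0.170, power 0.217 (about 0.25 by simulation).
- n = 165: SE = 0.0513, power 0.974.

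**Step 2: chance that the categories disagree**, meaning at least one interval excludes zero and at least one does not, although the true effect is the same in all: 1 − ∏pᵢ − ∏(1 − pᵢ). This was checked with 200,000 simulated trials per case. The last column is the simulated rejection rate of a direct test of equal risk differences at nominal 0.05.

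| Split, N = 360 | Per arm | Formula | Simulated | Direct contrast |
|---|---|---|---|---|
| 50/50 | 90, 90 | 0.295 | 0.303 | 0.052 |
| 70/30 | 126, 54 | 0.410 | 0.403 | 0.054 |
| 30 vs 330 | 15, 165 | 0.768 | 0.736 | 0.068 |
| three equal age bands | 60 each | 0.681 | 0.683 | 0.054 |

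For 30 vs 330 the formula is high because it understates the small group's power. With 0.25 it gives 0.25·0.026 + 0.75·0.974 = 0.737.

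**Step 3: how far this depends on the assumptions** (simulated).

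- N = 240: 45% for 50/50 and 69% for 30 vs 210.
- N = 360 with 41.8% on NAL ER, the smaller effect in SAP section 5.2: 44% for 50/50 and 75% for 30 vs 330.
- No drug effect (25% in both arms): about 10% for two categories and up to 16% for three, over N = 240 and 360.
- A difference read only when two intervals fail to overlap, N = 360 and 25% vs 45%: 0.6% for 50/50 and 2.4% for 30 vs 330.

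**Step 4: what a direct contrast can deliver.** For equal halves at N = 360 the SE of the difference of differences is √(2·0.435/90) = 0.0983. The half-width is 1.96·0.0983 = 0.193. Power for a 20-point difference in effect is Φ(0.20/0.0983 − 1.96) = Φ(0.074) = 0.53. Over seven factors (age, sex, five history groups), treated as independent, the chance of at least one false positive at 5% each is 1 − 0.95⁷ = 0.30.

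**The case against.** The strongest reply is that the SAP sets no decision rule. It never says that one interval excluding zero beside another including it counts as a difference, so an error rate for that reading belongs to the reader and not to the plan. That stands. A reader might infer that the plan itself produces false subgroup differences 30% to 74% of the time. The documents do not support this: the figures need the unstated reading rule, a homogeneous 20-point effect, N = 360 and assumed shares.

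Two further inferences also go too far. One is that disagreement is the usual result. For two-category factors with moderate splits at the planning rates it is 30-41% in the table, below half. The other is that almost every trial would show at least one factor in disagreement. That needs prevalences for the history groups, which the documents do not give and which SAP section 8.3.2 leaves to be settled before unblinding.

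It is also fair that categories of a factor are disjoint, so an unadjusted difference of differences can be worked out from the planned table. This does not remove the gap, since the plan does not ask for it, but it does make the repair cheap. The subgroup work lies outside the testing sequence and outside every stated objective, so nothing in the plan licenses a claim that NAL ER fails in some group.

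Last, adding an interaction to the repeated-measures code would need a three-way term with visit, in groups as small as about 15 per arm, and the SAP's version history already records convergence problems. That is a reason to use a Week 14-only analysis.

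**Conclusion.** The point holds as a mismatch between aim and method in an exploratory section. SAP section 8.6.2 asks whether results differ between subgroups, and no output in either document estimates or tests that.

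The size of the risk is conditional. It is about 30% (50/50) to 74% (30 vs 330) only if readers judge by whether each interval excludes zero, under a common 25% vs 45% effect at N = 360. Other effects and reading rules move it from about 1-2% to well above half. The direct contrast stays near 5-7% per factor. Nothing here touches the primary or key secondary conclusions. It is worth correcting because the correction is cheap and the present table is easy to misread.

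**What to change.** In SAP section 8.6.2, for each subgroup factor:

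1. Add an exploratory Week 14 treatment-by-subgroup contrast. The main measure is the difference between categories in the responder-rate difference, with 95% CI, because it is on the scale of the planned table. For the three age bands, give contrasts against a named reference band.
2. As support, give an interaction odds ratio with 95% CI from a logistic model on Week 14 data only. Equal effects on one scale need not be equal on the other, so say in advance that the risk-difference contrast is the main one.
3. Keep the within-category estimates, and state that a category interval including or excluding zero is not evidence of a subgroup difference.
4. Label the results as exploratory, low-powered (about 53% for a 20-point difference in effect between equal halves at N = 360) and unadjusted for multiplicity (about 30% chance of at least one false positive over seven independent factors).

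If the sponsor does not want a contrast, the minimum is to reword the aim as descriptive.

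The cost is a short SAP edit and one contrast and one model per factor on data already collected. The downside is wide intervals, about ±19 points for equal halves and wider for unequal groups, so the subgroup evidence will look weaker.

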8.6.3 Analysis of secondary efficacy endpoints

All secondary endpoints will be analyzed using the mITT population.

MMRM without imputation for missing data:

The following secondary efficacy endpoints will be analyzed using a mixed model for repeated measures (MMRM):

- The mean change in 7-day average WINRS from baseline to Week 14 for the NAL ER treatment arm versus the placebo arm;
- The mean change in ItchyQoL from baseline to Week 14 for the NAL ER treatment arm versus the placebo arm;
- The mean change in sleep disturbance (PROMIS Sleep Disturbance Short Form 8a) from baseline to Week 14 for the NAL ER treatment arm versus the placebo Arm.

The analysis of change from baseline to week 14 will be performed utilizing all observed data for visits up to and including Week 14, without imputation for missing data. The model used for this analysis will include the fixed effects of treatment, visit, treatment-by-visit interaction, and baseline value. An unstructured variance-covariance matrix will be used in the analyses. The comparison of interest is the treatment difference at Week 14. The model will provide least-squares mean estimates, standard errors, two-sided 95% confidence intervals and p-values for mean change at all time points between treatments (NAL ER vs. placebo) for ItchyQoL (total score and subscales: symptoms, functional limitations, emotions) and PROMIS. The same statistics will be provided for WI-NRS, except for the p-values.

Sample SAS code:

```
PROC MIXED data=xxxx;
  CLASS visit treatment subjid;
  MODEL CHG = treatment visit treatment*visit baseline/solution DDFM=KENWARDROGER;
  REPEATED visit / type=un subject=subjid;
  LSMEANS treatment*visit / pdiff CL;
  ODS output Diffs=outdata1 LSMeans=outdata2;
RUN;
```

Sensitivity analyses: MMRM with imputation for missing data

We will use the imputation methods described above for the primary efficacy endpoints to assess the sensitivity of missing data on inference regarding the secondary endpoints. Since these are continuous measures, we will use the delta methods described above.

Summary for Categorical Endpoints:

The count and percentage will be provided for the following endpoints:

- Change in PAS as assessed by the percentage of subjects having a 1-category improvement in the percentage of prurigenous lesions with excoriations/crusts (item 5a) from baseline to Week 14 for the NAL ER treatment arm versus the placebo arm;

- Change in PAS as assessed by the percentage of subjects having a 1-category improvement in the percentage of healed lesions (item 5b) from baseline to Week 14 for the NAL ER treatment arm versus the placebo arm;
- Change in PAS as assessed by the percentage of subjects having a 1-category improvement in the percentage number of lesions (item 2) from baseline to Week 14 for the NAL ER treatment arm versus the placebo arm;
- Change in IGA-PN as assessed by the percentage of subjects having a 1-category improvement in activity from baseline to Week 14 for the NAL ER treatment arm versus the placebo arm;
- Change in IGA-PN as assessed by the percentage of subjects having a 1-category improvement in stage from baseline to Week 14 for the NAL ER treatment arm versus the placebo arm;
- The proportion of subjects with PBI-P ≥ 1 at Week 14 for the NAL ER treatment arm versus the placebo arm;
- The proportion of subjects with PBI-P ≥ 2 at Week 14 for the NAL ER treatment arm versus the placebo arm;
- The proportion of subjects with PBI-P ≥ 3 at Week 14 for the NAL ER treatment arm versus the placebo arm.

In addition, shift tables from baseline for improved ≥ 1 , no change, worsened ≥ 1 , and discontinued at Week 14 will be presented for PAS (item 5a), PAS (item 5b), PAS (item 2), IGA-PN for Activity, and IGA-PN for Stage.

Logistic Regression for Categorical Endpoints

The logistic regression model used for the primary endpoint will also be used for several secondary efficacy endpoints. Subjects with missing Week 14 measurement are treated as non-responders. Response rate, standard error, OR between the treatment groups, 95% confidence interval and p-values will be provided. The endpoints are:

- Change in PAS as assessed by the percentage of subjects having a 1-category improvement in the percentage of pruriginous lesions with excoriations/crusts (item 5a) from baseline to Week 14 for the NAL ER treatment arm versus the placebo arm;
- Change in IGA-PN as assessed by the percentage of subjects having a 1-category improvement in activity from baseline to Week 14 for the NAL ER treatment arm versus the placebo arm (95% CI only, with no p-value).

Sensitivity analysis for PAS (item 5a)

The sensitivity analysis to assess the impact of concomitant medications use for the primary endpoint will also be used for PAS (item 5a).

For open-label period visits, descriptive statistics will be displayed by treatment and overall for all secondary variables.

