10.2.3 Blinding and Randomization of Study Treatments

Randomization will be performed by IWRS. Upon confirmation of eligibility by the study site, subjects will be randomized in a 1:1 ratio to either Arm 1 or Arm 2.

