13.2 Randomization

A randomization schedule will be computer-generated before the start of the study. After all screening procedures are performed and results of screening tests are available, eligible subjects will be activated in the IWRS, and assigned randomly on a 1:1 basis to the following treatment groups:

- Arm A: 162 mg NAL ER
- Arm B: Placebo

Randomization will be performed by the IWRS. Subjects will be stratified by site.

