13.4.6.2 Analysis of Secondary Endpoints

All secondary endpoints will be analyzed using the MITT population. The change from baseline in continuous endpoints (WI-NRS, ItchyQoL, PROMIS Sleep Disturbance Short Form 8a) up to Week 14 will be analyzed based on a mixed model for repeated measures analysis that includes the fixed effects of treatment, visit, treatment by visit interaction, and baseline value. The main treatment comparison of interest is at Week 14. For PAS, individual items will be presented with counts and percentages for categories by treatment group and visit; for excoriations/crusts, a logistic regression analysis will be performed for data at Week 14, with responders defined as subjects who had a ≥ 1 - category improvement from baseline. For IGA-PN, individual items (PN Activity and PN Stage) will be presented with counts and percentages for categories by treatment group and visit; a logistic regression analysis will be performed for PN Activity at Week 14, with

responders defined as subjects who had a ≥ 1 -category improvement from baseline. For PBI-P, the count and percentage of responders (defined as those with a PBI-score of ≥ 1 at Week 14) will be presented by treatment group. For open-label extension period visits, descriptive statistics will be displayed by treatment for all secondary variables.

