8.5 Efficacy analyses

8.5.1 Analysis methods

8.5.1.1. Logistic Regression Analysis

The primary efficacy endpoint (and other binary efficacy endpoints) “responder type” efficacy endpoints will be analyzed with a logistic regression model with baseline score as a covariate and site (USA versus other) as a fixed effect. The logistic regression model will provide estimated response rates, standard error, odds ratio (OR), two-sided 95% confidence interval for OR, and p-values at Week 14.

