8.5.1.2 Mixed model repeated measures analysis

A mixed model repeated measures analysis using ‘direct likelihood’ will be performed for continuous efficacy outcomes. The SAS procedure PROC MIXED will be used. The preferred model will include the fixed effects of treatment, visit, treatment-by-visit interaction, and the baseline value of the endpoint variable as a covariate. An unstructured matrix for the variance-covariance will be used. The denominator degrees of freedom will be calculated according to the Kenward-Roger method.

In case of non-convergence of the preferred model or memory issues, the following back-up models are defined:

1. The same as the preferred model, but the Kenward-Roger method will be replaced by Satterthwaite approximation.

2. The same as the preferred model, but with handling of the selection of the covariance structure for the final model in a hierarchical fashion, with the order being Toeplitz, AR (1), and compound symmetry, respectively.

The second back-up model will only be used if the first back-up model does not converge or has memory issues.

The model will provide least-squares mean estimates, standard errors, two-sided 95% confidence intervals and p-values (where applicable) for mean change at all visits between treatments (NAL ER vs. placebo).

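### Randomisation is stratified by site, but the MMRM for the continuous secondary endpoints has no site term; if site differences persist, its standard errors are slightly conservative

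*SAP*

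**What the plan says.** On allocation, Protocol 13.2 says "Subjects will be stratified by site". Protocol 10.2.3 gives only the ratio ("subjects will be randomized in a 1:1 ratio to either Arm 1 or Arm 2"), as does the SAP section on randomization and blinding. Neither document gives a block size.

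On the continuous endpoints, the documents agree with one another:

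- Protocol 13.4.6.2 describes a "mixed model for repeated measures analysis that includes the fixed effects of treatment, visit, treatment by visit interaction, and baseline value".
- SAP 8.5.1.2 says "The preferred model will include the fixed effects of treatment, visit, treatment-by-visit interaction, and the baseline value of the endpoint variable as a covariate".
- SAP 8.6.3 repeats those terms ("The model used for this analysis will include the fixed effects of treatment, visit, treatment-by-visit interaction, and baseline value"), and its sample code reads "MODEL CHG = treatment visit treatment*visit baseline/solution DDFM=KENWARDROGER". The CLASS statement lists visit, treatment and subject only.

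On the binary endpoints, Protocol 13.4.6.1 puts pooled site in the primary model as a random effect, because subjects at one site may be correlated. SAP 8.5.1.1 replaces this with a "logistic regression model with baseline score as a covariate and site (USA versus other) as a fixed effect". SAP section 9 records the move from random site to fixed region. It does not say why the MMRM has neither.

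**The concern.** A factor used to stratify allocation is normally carried into the analysis. Stratification balances the arms within site, so site-to-site variation largely cancels from the treatment difference. A model that ignores site still counts that variation as residual error, and the standard error it reports is then larger than the design warrants.

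The plan is also uneven. WI-NRS has a geographic term when it is analysed as responder status and none when it is analysed as a mean, although the patients and sites are the same. ItchyQoL and PROMIS are two of the three key secondary endpoints in Protocol 13.4.6.3, so precision on them matters. At stake are somewhat wide confidence intervals and a small loss of power.

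**Working it through.** **1. The plan's own figure.** Inputs from SAP 5 and 5.2: 25% versus 45% responders, two-sided 0.05, 90% power.

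n per arm = [1.96·sqrt(2·0.35·0.65) + 1.2816·sqrt(0.25·0.75 + 0.45·0.55)]² / 0.20² = 117.4, rounded up to 118, or 236 in total.

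The SAP has 234 without site and a target of 240 with site, so its figure reproduces. At 120 per arm I get 90.6% power, and 79.2% if the active rate is 41.8% (SAP: 80%). All of this concerns the binary primary endpoint. The documents give no SD, ICC, sample size or power for the three MMRM endpoints, so the effect on them can only be shown as a range.

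**2. Upper bound on the excess.** Let ICC be the share of baseline-adjusted variance that lies between sites. With perfect balance within site, the true variance of the treatment difference scales with (1 − ICC), while the model without site uses the whole variance. So f = SE without site / SE with site = 1/sqrt(1 − ICC). Actual alpha is 2·[1 − Φ(1.96·f)]. Power, where a site-adjusted test would have 90%, is Φ(1.96 + 1.2816 − 1.96·f).

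| Assumed ICC | f | Actual alpha | Power |
|---|---|---|---|
| 0 | 1.000 | 0.050 | 90.0% |
| 0.01 | 1.005 | 0.0489 | 89.83% |
| 0.02 | 1.010 | 0.0477 | 89.65% |
| 0.051 | 1.027 | 0.0442 | 89.05% |
| 0.10 | 1.054 | 0.0388 | 88.01% |

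**3. Where 0.051 comes from.** SAP 5.2 assumes 30 sites whose odds of response rise by a factor of 1.05 per step. The site SD on the logit scale is ln(1.05)·sqrt((30² − 1)/12) = 0.422, so the variance is 0.178. The latent-scale ICC is 0.178/(0.178 + π²/3) = 0.051. Carrying this over to continuous change scores is an assumption.

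**4. What about five patients per site does to it.** The Protocol synopsis gives about 70 centres and about 360 subjects: 360/70 ≈ 5 each. I simulated a Week 14 analysis of covariance with 70 sites and 360 subjects, 800 runs per setting. Assumed: blocks of 4, uneven site sizes, 20% missing, one fifth of site variance lying between regions. Entries are the mean model SE without site divided by the mean model SE with the term shown.

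| ICC | Random site | Unpooled fixed site | Region only |
|---|---|---|---|
| 0 | 1.00 | 0.95 | 1.00 |
| 0.02 | 1.01 | 0.96 | 1.00 |
| 0.05 | 1.02 | 0.97 | 1.01 |
| 0.10 | 1.04 | 1.00 | 1.01 |
| 0.20 | 1.10 | 1.06 | 1.02 |

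A value below 1 means that adding the term makes the standard error larger. The random-site column uses the true variances, so it is a best case. Without site, the rejection rate under the null ran from 0.038 to 0.056, which shows no inflation given a simulation error of about 0.008 (sqrt(0.05·0.95/800)). This is a single-visit stand-in for the MMRM. Empirical SEs carry Monte Carlo error of about 2.5%, so they cannot by themselves confirm a 2% excess.

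**The case against.** The strongest defence is that the model was pre-specified, is the same in both documents, and errs on the safe side. The size cannot be derived for these endpoints, because there is no ICC and no block size. The only site spread available belongs to another endpoint, and the SAP doubts it is that large. With about five patients per site, within-site balance is imperfect and dropout weakens it further. The obvious remedy, fitting the actual strata as fixed effects, would do harm at any ICC below about 0.10. The SAP has already moved away from random site effects, and its version history records convergence trouble. Finally, SAP section 9 says that ItchyQoL and PROMIS left the ranked testing order, and SAP 8.6.3 gives no p-value for mean WI-NRS change.

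Most of this stands, and it limits the point to a small one. Three parts do not remove it:

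- Agreement between the documents shows that the omission was planned; it gives no reason for it.
- The recorded convergence trouble led to the switch from PROC GLIMMIX to PROC GENMOD, which is the binary analysis, not this linear model.
- The ranking is itself inconsistent, since the list under Multiplicity still includes all three endpoints. That is a separate matter, and estimates with confidence intervals are reported either way.

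For the imputed data, the PROC MIXED template in SAP Appendix 12.3 is a placeholder that neither names nor rules out site.

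**Conclusion.** The MMRM leaves out the factor that randomisation was stratified on, and the plan does not say why. If site effects survive baseline adjustment and allocation is balanced within site, the standard errors are conservative by up to 1/sqrt(1 − ICC): about 0 to 5% for ICC 0 to 0.10. At the SAP's planning spread the figure is 2.7% as an upper bound and about 2% in the simulation, or about one point of power from 90%.

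A reader might infer that the standard errors are certainly too large. The documents do not support that, because both conditions are unverified. A reader might also convert the planning spread into lost patients: 360/(1 − 0.051) − 360 ≈ 19. That figure assumes perfect balance and borrows its ICC from a binary endpoint, so it is a ceiling under assumptions and not an estimate. Nor is this a validity fault: the omission causes no bias, and any effect on type I error is downward. It is a matter of modest precision and consistency.

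**What to change.** In SAP 8.5.1.2 and 8.6.3, add a random site intercept to the MMRM, or a pooled-site factor. Make the same change in the PROC MIXED code for observed data and in the Appendix 12.3 template for imputed data. If pooling is chosen, write the pooling rules before unblinding: Protocol 13.4.6.1 leaves them to the SAP, and the model sections of the SAP offer only a US-versus-other split or country. Name the current model as the fallback if the new one does not converge, placed in order with the back-up models already in 8.5.1.2.

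Do not fit unpooled fixed effects for about 70 sites. Do not rely on a US/Europe term alone: region was not the stratum, and it recovers about 1% or less at ICC up to 0.10. If the sponsor prefers to keep the model as it is, one sentence of justification in SAP 8.5.1.2 would close the point.

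The cost is a wording change, slightly more model complexity and, with pooling, a few degrees of freedom. No data collection changes.
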